## 2 STUDY OBJECTIVES

PARMA is a randomized, open-label, two-arm, phase 2A clinical trial testing two different  $\Delta P$  (defined as peak pressure minus PEEP) strategies in pediatric ARDS. We will compare a high  $\Delta P$  (25 cmH2O) versus low  $\Delta P$  (15 cmH2O) strategy on time to hypoxemia resolution (alive and PaO2/FIO2 > 300) while assessing effects on lung aeration by EIT.

### 2.1 Primary Objective (or Aim)

The primary objective of this study is to determine the whether the high  $\Delta P$  (25 cmH2O) strategy (intervention) reduces time to hypoxemia resolution in children > 2 weeks to 18 years, relative to a low  $\Delta P$  (15 cmH2O) strategy.

### 2.2 Secondary Objectives (or Aim)

The secondary objectives are to:

- Determine if there is a relationship between  $\Delta P$  strategy (25 or 15 cmH2O) with lung aeration determined by post-randomization EIT.
- Determine the relationship between  $\Delta P$  strategy (25 or 15 cmH2O) with VFDs at 28 days.
- Determine the relationship between  $\Delta P$  strategy (25 or 15 cmH2O) with mortality at 28 days, PICU discharge, and hospital discharge.
- Determine the relationship between  $\Delta P$  strategy (25 or 15 cmH2O) with new oxygen- or ventilator-dependency at discharge.
- Determine the relationship between  $\Delta P$  strategy (25 or 15 cmH2O) with new ventilator-associated pneumonia.
- Determine the relationship between  $\Delta P$  strategy (25 or 15 cmH2O) with new multiple organ dysfunction syndrome.
- Evaluate the tolerability and safety of the high  $\Delta P$  (25 cmH2O) strategy in pediatric ARDS.

### 3 INVESTIGATIONAL PLAN

#### 3.1 General Schema of Study Design (Figure 1)

Screening and Approach: All PICU patients will be screened twice daily during weekdays, and once daily on weekends, for presence of study eligibility criteria. Patients are initially screened using an existing EPIC functionality to identify new instances of mechanical ventilations, and additional screening of potentially eligible subjects will be performed by trained research assistants and coordinators. Eligible subjects will be approached within 24 hours of meeting eligibility criteria for trial participation and informed consent.

Intervention: Intervention will start immediately after randomization, with initiation of EIT and of randomized  $\Delta P$  strategy within 4 hours of consent. The Intervention Phase will continue until either the primary outcome or failure criteria are reached, withdrawal from the study, death, or 90 days from randomization.

Follow-Up: Follow-up will start once the Intervention Phase is finished and will continue until hospital discharge or 90 days post-randomization, whichever comes first.

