##### 3.1.2 Study Treatment Phase (start of the study intervention)

**Ventilator Protocol:** Subjects will have EIT (Timpel) bands placed and measurements taken at pre-randomization ventilator settings within 4 hours of consent. Randomized  $\Delta P$  treatment arm will be delivered by PCV, with peak pressures set according to  $\Delta P$  arm and PEEP assigned according to a PEEP/FIO2 grid. Specific ventilator management details are provided below.

Mode of mechanical ventilation	Pressure control ventilation (PCV) delivered using synchronized intermittent mandatory ventilation with pressure support (common and preferred mode in CHOP PICU) or assist control
$\Delta P$ (peak pressure minus PEEP)	
1) high <math>\Delta P = 25</math> cmH2O: initial <math>\Delta P</math> is set to 25 cmH2O, and adjusted between 20 and 30 cmH2O (in increments of 2 cmH2O) to keep <math>V_T \leq 10</math> mL/kg IBW
 
2) low <math>\Delta P = 15</math> cmH2O: initial <math>\Delta P</math> is set to 15 cmH2O, and adjusted between 10 and 20 cmH2O (in increments of 2

	cmH2O) to keep VT > 5 mL/kg IBW
Tidal volume (V T )	Kept between 5 and 10 mL/kg IBW (per ΔP parameters above)
Positive end-expiratory pressure (PEEP) and FIO 2 (assessed every 6 hours) to keep SpO 2 between 92% and 97%	Allowable PEEP/FIO2 combinations: FIO2: 0.30 to 0.40    0.41 to 0.55    0.56 to 0.80    0.81 to 1.0 PEEP: 5 to 8                    10 to 12                    12 to 14                    14 to 18
Respiratory rate	Adjust per pH goal; keep ≤ 50 breaths per minute
Pressure support	Match ΔP setting during Intervention Phase, even if able to wean respiratory rate, PEEP, or FIO2; adjust per ventilator weaning pathway if in Follow-Up Phase
Inspiratory time	Adjust to ensure inspiratory flow reaches zero
Plateau pressure monitoring	Inspiratory hold of 2 seconds every 12 hours
pH	Arterial pH ≥ 7.30; venous pH ≥ 7.25; respiratory rate and bicarbonate, but not ΔP, can be adjusted to achieve pH goals

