### 4.3 Subject Completion/Withdrawal

Successful Completion: Achievement of the primary outcome terminates the assigned ventilator protocol. After 28 days (timing of primary outcome), providers are encouraged but not mandated to continue with the assigned protocol. We will continue to gather data until hospital discharge up to 90 days after randomization.

Failure Criteria: Refractory hypoxemia or respiratory acidosis will typically prompt escalation to high frequency oscillatory ventilation or extracorporeal support, and will trigger a suspension of the assigned  $\Delta P$  protocol. In some cases, the clinical team may wish to cross over into pressures used in the alternative  $\Delta P$  protocol, which will still count as failure criteria. Subsequent ventilator management, including when weaning off of conventional or high frequency oscillatory ventilation or extracorporeal support, will be left to a physician's discretion. The CHOP PI ([name]) will record the primary reason for withdrawal. Every attempt will be made to continue data collection, providing that the family/patient concurs with continued data collection.

Early Termination: The assigned ventilator protocol can be suspended or permanently discontinued if, in the treating physician's judgment, it is no longer safe to continue. A protocol deviation will be documented only if the subject is withdrawn from the study due to a lack of protocol adherence absent clinical indication. Parents and legal guardians can also request withdrawal from the study and discontinue study procedures. Every attempt will be made to continue data collection, providing that the family/patient concurs with continued data collection.

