### 5.3 Safety Evaluation

Adverse events (AEs), whether anticipated or unanticipated, will be recorded according to the date of first occurrence, severity, and their duration. Notably, ARDS is a life-threatening condition for which we expect a wide range of events as part of the routine clinical course. Secondary Safety Endpoints include: pneumothorax requiring chest tube; acidosis requiring additional vasopressor support; protocol termination for failure criteria; other air leak not requiring chest tubes. Ventilator-

associated pneumonia; new or progressive multiple organ dysfunction syndrome are being recorded as secondary aims, and also serve as potential safety outcomes.

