## 8.6 Investigator Reporting of a Serious Adverse Event to Sponsor

An independent Medical Monitor will be appointed by the PI. The CHOP-based PI ([name]) and/or research coordinators will report SAEs that are both unexpected and probably or possibly related within 24 hours of becoming aware of the event, with a detailed completed report sent to the IRB and Medical Monitor within three working days of the event. The Medical Monitor will assess all SAEs. For each SAE that is both unexpected and probably or possibly related to study, [name] will provide sufficient medical history and clinical details for a safety assessment to be made with regard to continuation of the trial. The Medical Monitor will sign each SAE report after review. All SAE reports will be retained, and all SAE reports will be available for review by DSMB members and NICHD staff.

Event	Expected in pediatric ARDS	Serious adverse event	Pre-specified safety outcome
Death	Yes	Yes	Yes
Pneumothorax requiring chest tube	Yes	Yes	Yes
Other air leak not requiring chest tubes	Yes	Yes	Yes
Ventilator-associated pneumonia	Yes	Yes	Yes
New or progressive multiple organ dysfunction syndrome (increase in organ failure score or death 7 days after randomization)	Yes	Yes	Yes
Cardiac arrest	No	Yes	No
Arrhythmia	No	Yes	No
Hypotension	Yes	No	No
Need for extracorporeal membrane oxygenation	Yes	Yes	No

Need for renal replacement therapy	Yes	Yes	No
Brain herniation	No	Yes	No
New-onset seizures (without history of epilepsy)	No	No	No
Pulmonary embolus/deep vein thrombosis	No	Yes	No
Placement of new tracheostomy	Yes	Yes	No
Increase in vasopressor support due to acidosis	Yes	No	Yes
Protocol termination due to failure criteria	No	No	Yes

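### The protocol contradicts itself on the assigned ΔP between day 28 and day 90, and a permitted late departure could be read as a protocol failure

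*Protocol*

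**What the plan says.** **Length of the Intervention Phase.** Section 3.1 ends it at the primary outcome, failure, "withdrawal from the study, death, or 90 days from randomization". Day 28 is not on the list. Follow-Up begins only when the Intervention Phase is over.

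**A bedside rule tied to that phase.** The pressure-support row of the ventilator table in section 3.1.2 makes support match the ΔP "setting during Intervention Phase, even if able to wean respiratory rate", PEEP or FIO2. The weaning pathway applies to pressure support only in Follow-Up.

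**Status after day 28.** Section 4.3 states "Achievement of the primary outcome terminates the assigned ventilator protocol". After 28 days, "providers are encouraged but not mandated to continue with the assigned protocol".

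**Failure.** The failure paragraph of section 4.3 starts from refractory hypoxemia or respiratory acidosis. It then adds: "In some cases, the clinical team may wish to cross over into pressures used in the alternative" protocol, "which will still count as failure criteria". Section 5.3 lists "protocol termination for failure criteria" among the secondary safety endpoints. The event table in section 8.6 lists "Protocol termination due to failure criteria" as not expected, not serious, and a pre-specified safety outcome. Section 9.5 (Retention) follows primary, secondary and safety endpoints to discharge or day 90.

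**Schedule.** Table 1 marks the ventilator protocol and protocol compliance in columns that run to day 90.

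**The concern.** From day 28 to day 90 the assigned ΔP appears binding in one place and optional in another. The phase label decides whether pressure support stays tied to the assigned ΔP or follows the weaning pathway, so this is a conflict in bedside instructions and not only in terminology.

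The statistical interest lies in how a departure is then classified. Failure termination is a pre-specified safety outcome, the tolerability and safety of the high-ΔP strategy is a stated objective (section 2.2), and the DSMB reviews safety data without explicit stopping rules (section 4.4). If staff who use the latitude in section 4.3 generate entries in that outcome, it mixes failed ventilation with permitted discretion, and the mixture need not be the same in both arms.

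**Working it through.** The plan gives no figure on this point, so the check is mainly a comparison of texts.

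**1. Who is affected.** Resolution ends the assigned protocol (section 4.3), and death, failure and withdrawal end the Intervention Phase (section 3.1). The conflict therefore concerns only children alive, unresolved, ventilated and still on protocol after day 28, for at most 90 − 28 = 62 days.

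**2. The same child on day 29 under each text.**

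| Question | Sections 3.1 and 3.1.2 | Section 4.3 |
|---|---|---|
| Is the child in the Intervention Phase? | Yes, to day 90 unless another listed end occurs | Not addressed |
| Must the assigned ΔP continue? | Implied by the phase | Encouraged, not required |
| May pressure support follow the weaning pathway? | Only in Follow-Up, which has not begun | Implied if the protocol is dropped |

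No sentence ranks one text above the other.

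**3. How a discretionary stop would be classified.** Section 3.1 has no category for a provider who simply uses the day-28 latitude; the nearest listed ends are failure and withdrawal from the study. Early termination in section 4.3 covers a judgment that continuing is unsafe, which is a different event. The crossover sentence in section 4.3, taken by itself, has no time limit and states no indication. Because safety endpoints run to discharge or day 90, a crossover on day 35 falls inside the counting window.

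**4. Whether the arms are exposed equally.** Section 3.1.2 allows 20 to 30 cmH2O in the high arm and 10 to 20 in the low arm. A reduction below 20 puts a high-arm child into the low-arm range. A reduction in the low arm cannot enter the high-arm range. If late departures are mostly reductions, the high arm collects more apparent crossovers. If they are mostly increases, the direction reverses. The documents do not say which to expect.

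**5. Size.** The number of children is not stated. Two bounds help.

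- *Per child.* With 160 / 2 = 80 per arm, one reclassified child moves that arm's failure rate by 1 / 80 = 1.25 percentage points. Assuming 1, 5 or 10 such children in one arm, the shift is at most 1.25, 6.25 or 12.5 points.
- *Outer limit.* The event count is also not stated, so I found which counts fit the power in section 6.4. I used a normal approximation: prior on log HR with mean 0 and precision 10, information I = d/4 for d events, and success if the posterior probability of HR > 1 exceeds 0.90. Then c = 1.2816 × √((I + 10)/I), type I error = 1 − Φ(c), and power = Φ(ln 1.5 × √I − c). For d = 130: I = 32.5, c = 1.2816 × √(42.5/32.5) ≈ 1.466, type I error 0.0714, power 0.801. For d from 125 to 136, power runs from 0.787 to 0.818 and type I error from 0.0705 to 0.0724, in line with the stated 80% and 0.07. That leaves 160 − 136 = 24 to 160 − 125 = 35 children unresolved at day 28, *including those who have died*.

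The event count in the second bound is back-solved, so this does not reproduce the trial simulations. The affected children are a subset of the 24 to 35. The Abstract's mortality of up to 20% would be up to 0.20 × 160 = 32 deaths. Not all of these need precede resolution or day 28, but the comparison suggests that the living remainder is small.

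**The case against.** The strongest reply is that the texts can largely be read together. Section 3.1 gives an outer limit for a phase, and section 4.3 says how binding the protocol is within it; encouraging continuation presupposes that the protocol may run past day 28. Table 1 adds little, because its day-90 columns sit under the Follow-up heading and recording compliance while continuation is encouraged is not contradictory. This stands in part. It does not dispose of the pressure-support row, which attaches a rule to the phase label.

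A reader might also infer more than the documents support:

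- *Any move into the other arm's pressures is a failure.* The failure paragraph opens with refractory hypoxemia or acidosis. Section 3.1.2 ties failure to limits that cannot be maintained on the assigned ΔP, and section 9.4.2 ties it to unmet oxygenation or ventilation targets. Read with these, an elective change with targets met is not failure. The wider reading is open only because the crossover sentence carries no limit of its own.
- *Children are held on the assigned pressures for two more months.* Section 4.3 lets the physician suspend or stop when continuing is judged unsafe, and lets parents withdraw. Neither right lapses at day 28.
- *Permitted departures become protocol deviations.* Section 4.3 records a deviation only on withdrawal for non-adherence without clinical indication, which largely closes that route. The 70% adherence threshold in section 9.5 has no time window, but it only prompts action with study staff and is not an analysis rule.
- *Later mortality and dependency at discharge lose their meaning.* All analyses are by intention to treat (section 6.3.2), so they still compare the assigned strategies, including whatever discretion is allowed late on.

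An analysis plan, not at hand, might define the counting window for failure. It could not settle conflicting bedside instructions.

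**Conclusion.** The contradiction is real and unresolved within the protocol, but narrow. Section 3.1 and the pressure-support row treat days 28 to 90 as part of the assigned treatment; section 4.3 makes that treatment optional. The consequence for the data is a possible misreading, not an established bias: because the crossover sentence is unlimited and the safety window reaches day 90, a permitted departure could be entered as a failure termination, perhaps more often in the high-ΔP arm if late changes are mainly reductions.

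The size cannot be derived from the documents. It is 1.25 percentage points of one arm's failure rate per child, for a number that is not given and is probably small. With no failure rate stated either, nothing supports a claim that such cases could match the genuine failures in an arm. The primary outcome, 28-day ventilator-free days, 28-day mortality and the intention-to-treat comparisons are not affected. The point merits correction because the instructions conflict and the correction is cheap.

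**What to change.** 1. Reconcile section 3.1, the pressure-support row in section 3.1.2, section 4.3 and Table 1 so that all four give one status for the assigned protocol from day 28 to day 90. Which status applies is a clinical decision for the sponsor.
2. If departure after day 28 remains permitted, state that a discretionary departure, without refractory hypoxemia, acidosis or unmet targets, counts neither as failure termination nor as non-adherence. Put the corresponding limit in the crossover sentence of section 4.3.
3. Keep recording genuine failures after day 28, and report them separately from those up to day 28. Simply closing the failure count at day 28 would drop true late failures that section 9.5 says are followed to discharge or day 90.

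The cost is a wording amendment in those four places and one counting rule. No new visits or measurements are needed; the reason for stopping the assigned protocol must be recorded clearly enough to separate discretion from failure, and section 4.3 already has the investigator record a primary reason for withdrawal.

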##### 3.1.1 Screening Phase

All PICU patients will be screened twice daily (once on weekends) by trained study staff. Eligible patients will be approached  $\leq 24$  hours of meeting criteria, defined as time of second confirmatory hypoxemia measurement. The parents or legal guardians will be approached, and the trained staff members will engage them in a discussion regarding reasons for the study, study procedures, the risks and benefits, and answer all questions. Following the above conversation, written informed consent from each patient's parent/legal guardian agreeing to participate in this study will be obtained.

##### 3.1.2 Study Treatment Phase (start of the study intervention)

**Ventilator Protocol:** Subjects will have EIT (Timpel) bands placed and measurements taken at pre-randomization ventilator settings within 4 hours of consent. Randomized  $\Delta P$  treatment arm will be delivered by PCV, with peak pressures set according to  $\Delta P$  arm and PEEP assigned according to a PEEP/FIO2 grid. Specific ventilator management details are provided below.

Mode of mechanical ventilation	Pressure control ventilation (PCV) delivered using synchronized intermittent mandatory ventilation with pressure support (common and preferred mode in CHOP PICU) or assist control
$\Delta P$ (peak pressure minus PEEP)	
1) high <math>\Delta P = 25</math> cmH2O: initial <math>\Delta P</math> is set to 25 cmH2O, and adjusted between 20 and 30 cmH2O (in increments of 2 cmH2O) to keep <math>V_T \leq 10</math> mL/kg IBW
 
2) low <math>\Delta P = 15</math> cmH2O: initial <math>\Delta P</math> is set to 15 cmH2O, and adjusted between 10 and 20 cmH2O (in increments of 2

	cmH2O) to keep VT > 5 mL/kg IBW
Tidal volume (V T )	Kept between 5 and 10 mL/kg IBW (per ΔP parameters above)
Positive end-expiratory pressure (PEEP) and FIO 2 (assessed every 6 hours) to keep SpO 2 between 92% and 97%	Allowable PEEP/FIO2 combinations: FIO2: 0.30 to 0.40    0.41 to 0.55    0.56 to 0.80    0.81 to 1.0 PEEP: 5 to 8                    10 to 12                    12 to 14                    14 to 18
Respiratory rate	Adjust per pH goal; keep ≤ 50 breaths per minute
Pressure support	Match ΔP setting during Intervention Phase, even if able to wean respiratory rate, PEEP, or FIO2; adjust per ventilator weaning pathway if in Follow-Up Phase
Inspiratory time	Adjust to ensure inspiratory flow reaches zero
Plateau pressure monitoring	Inspiratory hold of 2 seconds every 12 hours
pH	Arterial pH ≥ 7.30; venous pH ≥ 7.25; respiratory rate and bicarbonate, but not ΔP, can be adjusted to achieve pH goals

**Adjustments to Ventilator Protocol:** Clinical teams will be given a protocol to assist with ventilator adjustments. At randomization, ventilator pressures will be set initially at either ΔP = 15 or 25 cmH2O, and VT assessed. The assigned ΔP treatment arm will be adjusted in increments of 2 to keep VT in the assigned range, if necessary. The clinical team will assess that the pressures (PIP and PEEP), VT, pH, and FIO2 limits are compliant with the assigned arm no less frequently than every 4 hours. Ventilator settings will be monitored continuously (as per usual care) by the clinical team, with instructions to contact the research team for any realtime concerns. The research team will monitor ventilator settings, compliance, and be available for discussion at least twice per day. The research team will assist the clinical team in the determination that the VT, pH, and FIO2 limits cannot be maintained with the assigned ΔP arm, triggering failure criteria (section 4.3 below).

**Other Procedures:** The PICU has existing protocols for sedation, fluid management, ventilator weaning, and extubation readiness. Specific strategies are detailed below.

Sedation	CHOP Sedation Pathway	Fentanyl and dexmedetomidine infusions to keep State Behavioral Scale (SBS) between -1 and 0 (moderate sedation)
Fluid management	CHOP Maintenance Fluid Pathway	Total fluid limit instituted to keep all non-resuscitation fluids (medications, feeds, blood products) to no exceed 1x maintenance; this will apply until a subject achieves full enteral nutrition

Ventilator escalation	Suggested	Escalation for refractory hypoxemia will be suggested in this order: 1) neuromuscular blockade infusion (required if PEEP $\geq$ 12 cmH 2 O), 2) inhaled nitric oxide, 3) prone positioning for 16 hours/day, 4) high frequency oscillatory ventilation, 5) extracorporeal support
Corticosteroids	Not protocolized	Corticosteroid use for ARDS is left to clinician discretion
Vasopressors	Not protocolized	Hemodynamic support strategies are left to clinician discretion
Nutrition and insulin	Not protocolized	Enteral or parenteral nutrition, and hyperglycemia management, will be left to clinician discretion
Renal replacement therapy and diuretics	Not protocolized	Use and mode of renal replacement therapy or diuretic use are left to clinician discretion
Ancillary therapy documentation	Required	While the order of use, or the decision to use, the above therapies are not mandated, all ancillary therapy use will be recorded daily
Ventilator weaning (may occur after Intervention Phase)	CHOP Ventilator Weaning Pathway	The CHOP PICU ventilator weaning pathway is initiated when there is spontaneous breathing, PEEP $<$ 12 cmH 2 O and FIO 2 $<$ 0.50; the pathway reduces respiratory rate, PEEP, and pressure support every 4 hours as tolerated until extubation readiness test
Extubation readiness (may occur after Intervention Phase)	CHOP ERT pathway (embedded in Ventilator-Weaning Pathway)	A spontaneous breathing trial (PEEP $\leq$ 8 cmH 2 O and pressure support $\leq$ 8 cmH 2 O for 1 to 2 hours) is initiated when PEEP $\leq$ 8 cmH 2 O and FIO 2 $\leq$ 0.40; an endotracheal tube leak is assessed and dexamethasone recommended for leak $>$ 20 cmH 2 O; subjects who pass this trial are extubated within 6 hours

**Electrical Impedance Tomography (EIT):** EIT is an FDA-approved non-radiating method of imaging lung aeration currently used at CHOP for clinical care, with an associated existing EPIC order. For PARMA, EIT will be performed post-randomization after stabilization of settings on the assigned  $\Delta P$  study arm and no later than 8 hours after initiation of assigned protocol. EIT measurements will be repeated 24 to 72 hours after initial post-randomization EIT measurements while on the assigned ventilator protocol. If the subject is off of the assigned protocol (i.e., failure criteria or early termination), the repeat EIT will be deferred. EIT images will not routinely be made available to the clinical team, as they require some significant offline processing.

